^a Visit/dosing windows of ±3 days on either side of the scheduled visits/dosing are permitted. In case of a delayed or missed dose, the investigator should return subjects on the original visit/dosing schedule in relation to Day 1 for subsequent doses. The window of ±3 days is relative to Day 1 and applicable for all subsequent visits/dosing. The minimum of time between doses should be no less than 4 days and no more than 10 days. Subjects do not need to return to the clinical site for dosing on weeks without study visits noted above if subject/caregiver completes study drug administration at home. See footnote “r” below.

^b Visit window of ±5 days. For subjects who prematurely discontinue study drug, the End of Treatment (EOT) visit should be completed within 14 days of withdrawal and follow-up visits should be completed at 8 weeks (Safety FU) and 14 weeks (PK & ADA FU) after the last dose of study drug, where possible. Subjects should continue to complete study assessments as outlined above where possible, with the exception of study drug administration. Anti-drug antibody sample and PK sample collection will not need to be completed if study drug is prematurely discontinued other than at the PK & ADA FU visit.

^c

All subjects who do not achieve cDAPSA low disease activity (cDAPSA ≤ 14) for 2 consecutive visits starting at Week 24 (e.g. at Week 20 and Week 24) will be required to discontinue study drug as described in Section 7.1. Participation in the study should be continued, with EOT visit and assessments as described in Section 4.1 and in footnote b and n.

^d Vital signs include measurements of temperature, respiratory rate, systolic and diastolic blood pressure, and pulse. Measurements should be taken in a sitting position after 5 minutes' rest.

^e Electrocardiograms in triplicate will be recorded (one minute apart) after subject has been supine for at least 5 minutes.

^f Chest x-ray (posterior/anterior or anterior/posterior) will be performed at screening in subjects who do not have a chest x-ray available within 3 months of screening. Women of childbearing potential must have a negative pregnancy test before an x-ray is performed.

^g Serious adverse events should be recorded from the signing of informed consent through the Safety Follow-up visit (ie, 8 weeks after the last dose of study drug); adverse events will be recorded from Day 1 (ie, administration of study drug) until 4 weeks after the last dose of study drug.

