9.3.5. Safety Analyses

Safety data will include summaries of exposure, AEs, TEAEs, SAEs, and laboratory data. No inferential statistics (*p*-values) will be reported for safety data.

Exposure will include the number of doses administered (including complete and incomplete doses) and reasons for missed or incomplete doses. Exposure will be reported through the planned collection of the primary endpoint and for the entire study. For subjects assigned to receive placebo who later receive izokibep, exposure will further be summarized by placebo and izokibep. Compliance will be summarized by placebo and izokibep and by phase (placebo controlled and after crossing over to active).

Adverse events and SAEs reported before the first administration of the study drug will be listed. All summaries will include only treatment-emergent events. The number of subjects who report 1 or more AEs, the number who report 1 or more severe AEs, the number who report 1 or more SAEs, and the number who report 1 or more AEs that lead to discontinuation of study drug will be summarized by treatment group during the primary phase of the study and overall. Subjects assigned to receive placebo who later receive izokibep will additionally be summarized by phase (placebo-controlled and after crossing over to active).

Laboratory data including ADAs will be summarized by treatment group and overall, at each planned collection timepoint.

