## 2. Protocol Details

### 2.1. Overall Study Design

This is a multicenter, randomized, double-blind, placebo-controlled, Phase 2b/3 Study to evaluate the clinical question of the effects of the efficacy and safety of izokibep in subjects with active psoriatic arthritis (PsA) who are tumor necrosis factor-alpha inhibitor (TNFi) naïve, who have had an inadequate response or intolerance to TNFi, or for whom TNFi is contraindicated. Approximately 325 subjects with active PsA will be enrolled. The study consists of up to a 28-day (4-week) screening period, a 51-week treatment period, and a follow-up period with visits at 8 weeks and 14 weeks after the last dose of study drug to assess safety and immunogenicity.

Subjects meeting eligibility criteria will be randomized into 1 of 4 treatment groups in a 4:4:4:1 ratio as follows:

- Group 1 (n=100): placebo every week (QW) from Day 1/Week 0 to Week 15, then izokibep 160 mg QW from Week 16 to Week 51.
- Group 2 (n=100): izokibep 160 mg QW from Day 1/Week 0 to Week 51.
- Group 3 (n=100): izokibep 160 mg every 2 weeks (Q2W) from Day 1/Week 0 to Week 50, with matching placebo Q2W until Week 51 for the weeks in between izokibep doses to maintain the blind.
- Group 4 (n=25): izokibep 80 mg every 4 weeks (Q4W) from Day 1/Week 0 to Week 48, with matching placebo QW until Week 51 for the weeks in between izokibep doses to maintain the blind.

Randomization will be stratified by prior TNFi use (Yes/No) and enthesitis (Leeds Enthesitis Index [LEI] > 0/LEI = 0). Anticipated enrollment of subjects previously treated with TNFi is 20% to 30%. The number of subjects without enthesitis entering into the study (LEI = 0 at baseline) will be capped at 70%.

Subjects will complete study assessments according to the study visits outlined in the Schedule of Activities (SoA) in the protocol. The primary endpoint will be assessed at Week 16. The last dose of study drug will be administered on Week 51.

Starting at Week 24, subjects who do not meet clinical Disease Activity for PsA (cDAPSA) low disease activity (cDAPSA  $\leq$ 14) at 2 consecutive visits (e.g. at Week 20 and Week 24) will be discontinued from study drug and can receive standard of care as deemed appropriate by the investigator.

An End of Treatment (EOT) visit will be conducted at Week 52. A Safety Follow-up visit will be conducted at Week 59. A pharmacokinetic/anti-drug antibody (PK/ADA) Follow-up and

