#### 5.1.3. Treatment Period

Data collected on Day 1 will be assigned to the Treatment Period unless the time (HH:MM) of data collection and time (HH:MM) of the first dose of study drug are both recorded and the data collection time is before the time of the first dose of study drug. In this case, the assessment will be assigned to the screening period. If the time (HH:MM) of data collection is not recorded but the protocol and/or eCRF includes an instruction to the effect that all Day 1 assessments are to be performed prior to the first dose of study drug, the data collected at Day 1 will be assigned to the screening period. However, adverse events and concomitant medications starting on Day 1, will be assigned to the Treatment Period, unless the time (HH:MM) demonstrates otherwise.

The Treatment Period is defined as the period from the date/time of the first dose of study drug to Week 52 (one week after the last dose) or early termination (end of treatment visit

should be completed within 14 days of withdrawal and follow-up visits should be completed at 8 weeks and 14 weeks after the last dose of study drug, where possible).

Treatment will be divided into two periods, Period 1 and Period 2, Period 1 will start at the first dose of study drug and ends at Week 16 when Week 16 assessments are completed and before administration of study drug. Period 2 will start at the time of administration of study drug at Week 16 and end at Week 52 or early termination/end of treatment visit.

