### 6.7.2. Adverse Events

All SAEs will be collected from the signing of the ICF until the 8-week follow-up visit. All AEs will be collected from the first dose of study drug until 4 weeks after the last dose of study drug. All AEs recorded on the eCRF will be coded using the latest MedDRA dictionary around the time of Database Lock and classified as either AEs or treatment-emergent AEs (TEAEs) as follows:

- TEAEs are either events with start date and time after the start of the Treatment Period and up to 4 weeks after the end of the Treatment Period, or events with start date and time prior to the start of the Treatment Period whose severity worsens on or after the start of the Treatment Period. TEAEs for period 2 are either events with start date and time after the start of administration of Week 16 treatment and up to 4 weeks after the end of the Treatment Period, or events with start date and time prior to the start of administration of Week 16 treatment whose severity worsens on or after the start of administration of Week 16 treatment. For subjects who receive treatment in period 2, TEAEs with start date after the start of period 2 will be assigned to period 2 only, not to period 1.
- Treatment-Emergent Serious AEs (TESAEs) will be defined as TEAEs which meet the criteria as Serious = “Yes”.
- The relationship between a TEAE and treatment is assessed as related or not related. A treatment-related TEAE will be defined as a TEAE considered by the investigator as related to treatment or with unknown/missing relationship to treatment.
- Assessment of AE severity will be based on eCRF AEs form.
- TEAEs leading to discontinuation of treatment are defined as TEAEs where “Action Taken with Study Treatment” is indicated as “Drug Withdrawn”.

In addition to the aforementioned AE types, the following TEAEs of special interest will be monitored:

- Candida infection,
- Inflammatory bowel disease,
- Suicidal ideation.
- Malignancies
- MACE (major adverse cardiovascular and cerebrovascular events: cerebrovascular accident and transient ischemic attack, non-fatal myocardial infarction or unstable angina, cardiovascular death)
- Tuberculosis (TB)
- Infections (serious, opportunistic, or fungal only)
- Cytopenias

- Systemic hypersensitivity reaction

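### Non-fatal SAEs starting in about the last three weeks of SAE collection (Weeks 56 to 59 for completers) enter no SAE incidence table that the SAP specifies

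*SAP*

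**What the plan says.** **Collection.** SAP 6.7.2: "All SAEs will be collected from the signing of the ICF until the 8-week follow-up visit". Protocol 1.3 (Schedule of Activities, footnote g) likewise has SAEs recorded "through the Safety Follow-up visit (ie, 8 weeks after the last dose of study drug". SAP 2.1 fixes the dates for a subject who stays on drug: "The last dose of study drug will be administered on Week 51" and "A Safety Follow-up visit will be conducted at Week 59". All other adverse events are collected only to 4 weeks after the last dose.

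**Classification.** SAP 5.1.3 defines the Treatment Period as running "from the date/time of the first dose of study drug to Week 52 (one week after the last dose) or early termination". SAP 6.7.2 makes an event treatment-emergent if it starts "after the start of the Treatment Period and up to 4 weeks after the end of the Treatment Period". A second limb admits events that began before treatment (or, for Period 2, before the Week 16 dose) and later worsened; it has no end date. A serious treatment-emergent event is one that meets this definition and is also marked serious.

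**Reporting.** All serious-event rows in SAP 6.7.2 are of serious treatment-emergent events: the overview, the tables by system organ class and preferred term, those for related events and for events leading to discontinuation or death, and the Period 2 groupings. So is the dedicated serious listing. Three outputs are wider or may be: the listing of all adverse events (with a treatment-emergence flag), the count and listing of deaths, and a listing of special-interest events worded as AEs.

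**Broader statements.** Protocol 9.3.5 says "All summaries will include only treatment-emergent events". The Protocol 1.1 synopsis, under Statistical Considerations, undertakes to summarize the percentage of subjects with each SAE, as an item alongside treatment-emergent events. Protocol 9.4 and SAP 6.7.7 both say that safety data will be summarized in full to the end of the study.

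**The concern.** The trial follows SAEs for longer than other adverse events, but its serious-event tables inherit a window that fits the shorter collection. A serious infection or a new bowel-disease diagnosis starting seven weeks after the last dose would be reported by the site and entered in the database, yet would add nothing to an SAE incidence table. Someone reading only the tables would take them to cover the whole SAE follow-up.

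The secondary safety objective names SAEs as an item separate from treatment-emergent events, and two passages promise summaries to the end of the study. The specified tables do not deliver that.

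**Working it through.** This is calendar arithmetic.

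**1. The plan's own figure.** Last dose at Week 51 (SAP 2.1), SAE collection for 8 weeks: 51 + 8 = Week 59. This matches the stated Safety Follow-up visit.

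**2. Close of the window for completers.** Treatment Period ends at Week 52 (SAP 5.1.3), plus 4 weeks (SAP 6.7.2): 52 + 4 = Week 56.

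**3. Gap for completers.** 59 − 56 = 3 weeks, or 21 days. With the ±5-day visit window in Protocol 1.3 it is 16 to 26 days. As a share of post-dose SAE collection: 3/8 = 38% of calendar time.

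**4. Non-serious events.** Collection ends 4 weeks after the last dose: 51 + 4 = Week 55, inside the Week 56 limit. The mismatch affects SAEs only.

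**5. Subjects who stop drug early.** Two readings of SAP 5.1.3 are possible.
- The Treatment Period ends at the End of Treatment visit. Assume that visit falls 0 to 14 days after the last dose. The window then closes on day 0 + 28 = 28 to day 14 + 28 = 42, while SAE collection ends on day 56. The gap is 56 − 42 = 14 days to 56 − 28 = 28 days.
- The Treatment Period runs to Week 52 because the subject stays in the study. The window again closes at Week 56. With the last dose in Week L, SAE collection ends at Week L + 8, so there is no gap whenever L + 8 ≤ 56, that is L ≤ 48.

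**6. Likely number of events.** Upper bound on person-time, if all 325 planned subjects complete: 325 × 3 = 975 person-weeks, and 975/52 = 18.75 person-years. The documents give no SAE rate, so assume 2 to 10 per 100 person-years: 18.75 × 0.02 = 0.4 to 18.75 × 0.10 = 1.9 events over all four arms.

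**7. Remaining drug.** Protocol 2.2.3.4 gives a geometric mean half-life of 278 h (11.6 days) after single subcutaneous doses, with individual values of 199 to 464 h. Assuming simple exponential decline from the last dose and ignoring absorption, the fraction left is 2^(−days/half-life).

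| Time | 278 h | 199 to 464 h |
|---|---|---|
| Week 56 (day 35) | 12% | 5% to 29% |
| Week 59 (day 56) | 3.5% | 1% to 13% |

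On these assumptions some drug remains during the untabulated weeks in most subjects, but the amount varies widely.

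**The case against.** The strongest reply is that a treatment-emergent window shorter than SAE collection is a legitimate analysis choice. Protocol 9.3.5 itself restricts summaries to treatment-emergent events, and the synopsis also describes SAE incidence over 52 weeks. The protocol therefore does not speak with one voice. That stands: this is a mismatch to be reconciled, not a plain error in the definition.

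Four stronger readings are tempting, and the documents do not support them.

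- *Late SAEs are lost, or all of them drop out of every count.* They remain in the listing of all adverse events. Deaths are counted and listed without a treatment-emergent limit. The special-interest listing is worded as AEs, although SAP 6.7.2 elsewhere speaks of treatment-emergent events of special interest, so its scope is not certain. Late worsening of an event that began before treatment can still qualify.
- *Early discontinuers always lose 2 to 4 weeks.* This needs the first reading in step 5. SAP 5.1.4 links the early termination visit to leaving the study, and Protocol 7.1 encourages subjects who stop drug to stay. The End of Treatment visit is also timed from withdrawal, not from the last dose.
- *38% of post-treatment SAEs are dropped.* The figure is a share of calendar time, not of events.
- *The treatment-emergent definition must be extended to 8 weeks.* Protocol 6.8.3 and 7.1 allow other therapy once study drug is permanently stopped, so a longer window could label events arising on other treatment as emergent. It would also put two windows into one overview table.

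What survives is narrower: none of these outputs puts a non-fatal, new-onset late SAE into an incidence table.

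**Conclusion.** The point holds for completers and follows directly from the SAP's definitions. SAEs are collected to Week 59, the onset-based window closes at Week 56, and all specified serious-event tables stop there. About 3 weeks of collected non-fatal SAEs are left to listings, short of what the synopsis and the end-of-study statements in Protocol 9.4 and SAP 6.7.7 lead a reader to expect.

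The practical size is probably small: about two events at most under the assumed rates. For completers these fall after the placebo-controlled period, so the 16-week comparison is untouched. For subjects who stop drug early, a gap of 14 to 28 days is conditional on where their Treatment Period ends, which SAP 5.1.3 leaves unclear. If a subject who stops during Period 1 has that gap, it could reach the placebo-controlled safety comparison. The efficacy conclusions are not affected. This is a cheap improvement to the reporting plan.

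**What to change.** In SAP 6.7.2, add one table, by system organ class, preferred term and treatment group, and one listing, of all SAEs with onset from the first dose through the 8-week Safety Follow-up visit. Flag events outside the treatment-emergent window in both. Leave the treatment-emergent definition unchanged. The table then supplies the all-SAE summary however the end of the Treatment Period is read for early discontinuers. Reconcile Protocol 9.3.5 with the synopsis and Protocol 9.4 so that the wider SAE table is expressly allowed.

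The cost is one more table and listing from data already collected, with no new visits and no effect on alpha. SAE counts may be slightly higher than in the treatment-emergent tables. Some added events may follow a switch to other therapy, so a footnote should say so.

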8.3.6. Events of Special Interest

Based on the class effects or potential risks with IL-17 inhibitors, the following events of special interest (preferred term) will be monitored:

- Candida infection
- Inflammatory bowel disease.

In addition, based on the potential risk with an IL-17 receptor inhibitor the following events of special interest will also be monitored:

- suicidal ideation
- malignancies
- MACE (major adverse cardiovascular and cerebrovascular events : cerebrovascular accident and transient ischemic attack, non-fatal myocardial infarction or unstable angina, cardiovascular death)
- TB
- infections (serious, opportunistic, or fungal only)
- cytopenias
- systemic hypersensitivity reactions.

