Adverse events of special interest will be identified manually. After all data are entered into the database and before database unblinding, a list of all unique PTs will be generated. ACELYRIN pharmacovigilance and clinical development representatives will review the list and determine which are TEAEs of special interest in each category listed above. This determination will be documented in a memo, signed and dated before database lock, and stored in the study trial master file. The database will not be unblinded until the memo is finalized and signed.

Adverse events will be summarized by default descriptive summary statistics for categorical variables for the Safety Analysis Set as follows:

- An overview of TEAEs including the number and percentage of subjects with at least one of each mentioned TEAE type according to both Period 2 groupings as described in section 6.7:
  - Any TEAE
    - Leading to discontinuation of study treatment
    - Mild (Grade 1)
    - Moderate (Grade 2)
    - Severe (Grade 3)
    - Life-threatening (Grade 4)
    - Death (Grade 5)
    - Any TEAE
      - Grade 2 or higher
      - Grade 3 or higher
      - Grade 4 or higher
  - Any study treatment related TEAE
    - Leading to discontinuation of study treatment
  - Any serious TEAE
    - Leading to discontinuation of study treatment
    - Leading to death
  - Any serious study treatment related TEAE
    - Leading to discontinuation of study treatment
    - Leading to death
- The number and percentage of subjects reporting each TEAE and the count of number of events will be summarized by SOC and PT for the following types of TEAEs.
  - TEAEs
  - TEAEs of Special Interest
  - TEAEs Leading to Discontinuation of Study Treatment

- TEAEs leading to interruption of study treatment
- TEAEs by Maximum Severity
- TEAEs by Relationship to Treatment
- TEAEs by Relationship and Maximum Severity
- Study Treatment related TEAEs
- Study Treatment Related TEAEs Leading to Discontinuation of Study Treatment
- Serious TEAEs
- Serious TEAEs Leading to Discontinuation of Study Treatment
- Serious TEAEs Leading to Death
- Study Treatment Related Serious TEAEs
- Study Treatment Related Serious TEAEs Leading to Discontinuation of Study Treatment
- Study Treatment Related Serious TEAEs Leading to Death
- The number and percentage of subjects reporting each TEAE and the count of number of events will be summarized by SOC and PT for two subgroups:
  - Subjects < 65 years of age at baseline

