  - Subjects  $\geq$  65 years of age at baseline
- The number and percentage of subjects who died will be summarized
- The number and percentage of subjects reporting each TEAE and the number of events will be summarized by PT for all TEAEs
- The number and percentage of subjects reporting each TEAE and the number of events will be summarized by PT for TEAEs of Special Interest
- The number and percentage of subjects reporting each TEAE and the count of number of events according to the 5 Period 2 groupings as described in section 6.7 will be summarized by SOC and PT for the following types of TEAEs.
  - All TEAEs
  - Serious TEAEs

In the above summaries, subjects with more than one TEAE within a particular SOC are counted only once for that SOC. Similarly, subjects with more than one TEAE within a particular PT are counted only once for that PT.

For summaries by maximum severity, subjects with multiple TEAEs within a particular SOC or PT will be counted under the category of their most severe TEAE within that SOC or PT. TEAEs with missing severity will be included in the counts as severe (Grade 3) unless the TEAE has an outcome of fatal; in that case, the TEAE with missing severity will be included in the counts as death (Grade 5).

Summaries by SOCs and PTs will be sorted by SOCs by their Internationally Agreed Order (MedDRA) and PTs within SOC by descending order of total incidence. Where PTs tie, PTs will be sorted alphabetically.

All AE data will be listed and AEs and TEAEs will be presented together. Treatment-emergence status will be flagged in the listing. The listing will present the relative start and stop day of the AE calculated relative to the first dose of treatment and will be presented for those subjects who received at least one dose of treatment. If the AE is “Ongoing” it will be indicated as such in the listing and the relative stop day will not be calculated. Only original dates will be presented in the listing even though the relative day may be based on an imputed date.

In addition, the following listings will be presented:

- Listing of Deaths
- Listing of TEAEs
- Listing of Serious TEAEs
- Listing of AEs Leading to Interruption of Study Treatment
- Listing of AEs Leading to Discontinuation of Study Treatment
- Listing of AEs of Special Interest

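### Special-interest events are chosen from a list of preferred terms, but serious infection and cardiovascular death depend on the individual event, so these counts may be over- or understated

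*SAP*

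**What the plan says.** SAP 6.7.2 opens its selection procedure with "Adverse events of special interest will be identified manually". It then says what is reviewed: once data entry is complete and before unblinding, "a list of all unique PTs will be generated", and pharmacovigilance and clinical development staff of the sponsor "review the list and determine which are TEAEs of special interest in each category listed above". A memo, signed before database lock, records the outcome, and unblinding waits for it.

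Two of the categories listed just before this carry conditions on the event:

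- **Infections.** SAP 6.7.2 has "Infections (serious, opportunistic, or fungal only", matching Protocol 8.3.6, "infections (serious, opportunistic, or fungal only".
- **MACE.** The definition includes "non-fatal myocardial infarction or unstable angina, cardiovascular death".

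The selected events feed three outputs in SAP 6.7.2: a summary by SOC and PT, a summary by PT, and a listing.

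The same section already uses the event-level fields for other purposes. Treatment-emergent serious events "will be defined as TEAEs which meet the criteria as Serious" = Yes. Missing severity is imputed as grade 3 "unless the TEAE has an outcome of fatal", in which case it becomes grade 5.

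**The concern.** A list of unique PTs has one row per term and shows neither seriousness nor outcome. Protocol 10.3.3 (assessment of severity) says that seriousness is judged from what happened to the subject in the event. The same infection term can therefore be serious in one subject and non-serious in another. A mark placed on the term cannot separate the two, and no step in SAP 6.7.2 or Protocol 8.3.6 adds the Serious flag, the outcome or a case review to the selection.

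At stake is whether the AESI tables and listing show what their category names promise. If common infection terms are marked, non-serious cases swell the infection rows and can dilute a difference between arms in serious infections. If they are left unmarked, serious cases drop out. A cardiovascular death coded to an unmarked term would be missing from MACE.

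**Working it through.** The plan gives no figure on this point, so there is none to reproduce. The check is of the rule itself, followed by illustrations with assumed counts.

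**1. What a term-level mark does.** Take an infection PT that is neither opportunistic nor fungal, with n events of which s are serious. The category should count s.

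- PT marked: n counted, an excess of n − s.
- PT unmarked: 0 counted, a shortfall of s.
- Either choice is exact only if all events share the attribute (s = n when marked, s = 0 when unmarked).

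For a PT that is opportunistic or fungal by its meaning, every event qualifies, and the term-level mark works.

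**2. Size in one arm.** The arm size of 100 is planned (Protocol 4.1). The counts are assumed: one event per subject and one serious case, so the correct figure is 1/100 = 1%.

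| Subjects with the PT (n) | Correct | PT marked | PT unmarked |
|---|---|---|---|
| 2 | 1% | 2% | 0% |
| 5 | 1% | 5% | 0% |
| 7 | 1% | 7% | 0% |
| 10 | 1% | 10% | 0% |

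**3. How often a term would be mixed.** If each event under a PT is independently serious with probability p, the chance that the PT holds both kinds is 1 − pⁿ − (1 − p)ⁿ. The documents give no p for infections. The values below are assumptions, shown as a range.

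| Events under the PT (n) | p = 2% | p = 5% | p = 10% |
|---|---|---|---|
| 2 | 0.039 | 0.095 | 0.180 |
| 5 | 0.096 | 0.226 | 0.409 |
| 10 | 0.183 | 0.401 | 0.651 |
| 20 | 0.332 | 0.642 | 0.878 |

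A rarely reported term will probably not be mixed. A commonly reported one may well be.

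**4. Cardiovascular death.** The structure is the same. A death from a cardiovascular cause may be coded to a term outside the conditions named in the MACE definition. If that term is unmarked, the death is missed. If it is marked in order to catch the death, every other event under it enters MACE too.

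**5. What the other outputs supply.** SAP 6.7.2 also tabulates serious TEAEs by SOC and PT, tabulates serious TEAEs leading to death, counts and lists deaths, and lists serious TEAEs. Serious infections by arm can therefore be read elsewhere. The number of subjects with an infection that is serious, opportunistic or fungal cannot: adding the serious-infection row to the opportunistic and fungal rows counts a subject twice if both apply.

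**6. Comparison within the SAP.** For the last criterion for drug-induced liver injury, SAP 6.7.3.1 has medical professionals review the AEs of individual subjects and file a memo before lock and unblinding. The SAP thus already plans event-level review of this kind.

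**The case against.** The best defence is that the text omits a programming detail and does not state a wrong rule. Identification is called manual, the infection category itself carries the restriction to serious, opportunistic or fungal events, and nothing says that every event under a marked term counts regardless of seriousness. It is also fair that the AESI summaries are descriptive (Protocol 9.3.5 excludes p-values for safety), that serious events and deaths appear elsewhere, and that Protocol 2.2.3.3 reports no serious adverse events up to Week 16 in the earlier psoriatic arthritis trial.

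Most of this stands as a limit on the harm. It does not remove the gap, because the only object the SAP gives the reviewers is the list of terms, and the memo fixes a choice among terms. Protocol 8.3.6 attaches the preferred-term label only to the Candida and inflammatory bowel disease group, so it does not require term-level selection for infections or MACE.

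A reader might infer more than the documents support:

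- **That the AESI tables are bound to be wrong.** An error needs a mixed infection term, or a cardiovascular death under an unmarked term. Neither is certain.
- **That non-fatal myocardial infarction is misclassified.** A fatal infarction would also fall in MACE, as a cardiovascular death, so marking the infarction term puts the event in the right category either way. The SAP plans no split by MACE component.
- **That cytopenias are missed.** SAP 6.7.3 already grades laboratory values by CTCAE and tabulates the grades.
- **That these are established class risks of the drug.** Protocol 8.3.6 lists infections and MACE under a potential risk seen with an IL-17 receptor inhibitor. The events it ties to IL-17 inhibitors are Candida infection and inflammatory bowel disease.

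**Conclusion.** The point holds for two categories. The selection method in SAP 6.7.2 cannot by itself deliver serious infections or cardiovascular deaths, because both are attributes of the event and the method works on terms. The infection rows may be inflated or may omit serious cases whenever an infection PT that is neither opportunistic nor fungal has both kinds, and a cardiovascular death under an unmarked PT may be missed.

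The size depends on counts that the documents do not give. With assumed serious shares of 2% to 10%, a PT with 10 events has a chance of 0.183 to 0.651 of being mixed. No hypothesis test, endpoint or stopping rule is affected. The separate outputs on serious events and deaths limit the harm but do not replace the combined category count. It is worth correcting before unblinding, since an event-level rule chosen afterwards would be open to the charge that it was fitted to the result.

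**What to change.** In SAP 6.7.2, and in the memo already planned before unblinding, state:

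- **Infections of special interest** = (infection PT and Serious = Yes) or a PT on the opportunistic/fungal list.
- **MACE** = events under the selected PTs, plus any fatal event judged cardiovascular on blinded review of the individual event.
- **Other categories** stay with PT selection where the term defines the category, such as Candida infection, inflammatory bowel disease, tuberculosis and malignancies.

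The cost is a few lines of wording and a small programming change. The SAP already uses the seriousness and outcome fields. The one added task is a short blinded review of fatal events, which can be done while the PT list is being reviewed.
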